1.1. Study Objectives

Specific Aims

1. Determine the effect of progressive nicotine content reduction on nicotine and its metabolites and other biomarkers of smoking exposure.
 - a. Determine the effects of RNC (reduced nicotine content) cigarettes in both black and white smokers of lower SES (socioeconomic status) over an 18 week trial period. Subjects will be randomized to either, (i) gradual reduction in reduced nicotine content cigarettes, or (ii) cigarettes containing the nicotine content of their usual brand. It is expected that the gradual reduction of nicotine from progressively lowering nicotine exposure will lead to lower levels of blood nicotine metabolites and nicotine-derived 4-(methylnitrosamino)-1-(3-pyridyl)-1-butanol)(NNAL), while not affecting cigarettes smoked per.
 - b. Determine the modifying effect of menthol on progressive nicotine content reduction and biomarkers. It is expected that menthol will not modify the effect of progressive RNC cigarettes on the above biomarkers.
2. Determine the predictors of participant drop-out/relapse. We hypothesize that compensatory smoking behavior as measured by smoking topography and expired carbon monoxide (CO), a higher baseline nicotine dependence behavioral score, will be associated with dropout/ relapse.
3. Determine if a gradual reduction in RNC cigarettes vs. same nicotine content is associated with a reduction in stress. Psychological stress and nicotine stimulate the production of cortisol, a biomarker of stress pathways. It is expected that nicotine reduction will lead to initially higher levels

of psychological stress and cortisol associated with withdrawal but lowered levels of psychological stress/cortisol with long-term nicotine reduction.

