The FSPTCA is based on the premise that making tobacco less or non-addictive will result in a reduction in harm from tobacco smoke [27, 28]. This premise would apply for all aspects of nicotine dependence including smoking onset in non-addicted youths and smoking cessation in current dependent smokers. Although it is well known that compensatory smoking behavior (e.g. more frequent puffs or inhaling deeper) limits the ability to reduce nicotine exposure, at least in commercially available higher nicotine cigarettes [29], the feasibility of progressively switching to low nicotine cigarettes was considered to be technically feasible by the American Medical Association and other authoritative groups [28, 30]. A broad-based policy needs to consider the diverse population of smokers who vary substantially by socio-demographic, economic and cultural factors that may affect nicotine dependence and the choice of tobacco products smoked. In an initial report by Benowitz et al. [4] of a randomized trial of a specially blended low nicotine cigarette with features similar to Marlboro brand cigarettes, 130 smokers progressively lowered their nicotine over a 6-month period. There was a concurrent decrease in exposure to nicotine or nicotine derived carcinogen biomarkers such as cotinine and NNAL. In this trial, the mean level of education in participants was college graduation (e.g. ~15-16 years of education) and nearly all subjects were white. A similar trial by Hatsukami et al. [2] of 165 smokers that used commercially available Quest cigarettes assigned to two different low nicotine cigarettes for 6 weeks had similar findings.

A potential policy measure of lowered nicotine exposure through reduced nicotine yield cigarettes needs to specifically address whether lowered nicotine tobacco products reduces nicotine exposure given that smokers undertake compensatory smoking behaviors to maintain constant nicotine intake. The policy also requires that reduced nicotine cigarettes not increase exposure to tobacco smoke toxins and carcinogens, as well as decrease the levels of physiological dependence and smoking behaviors associated with nicotine dependence. This needs to be documented prior to the full endorsement of the policy [28] and will be the major focus of this proposal.

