9.2. Statistical methods

Basic baseline statistics including means (SDs) and frequency distributions (percentages) will be reported for demographic characteristics, subjective and objective measures (such as smoking history, the number of cigarettes and other nicotine products, and smoking topography measures). Where necessary, some characteristics will be reported by the two groups under investigation. Numerical baseline characteristics will be compared between the two groups using two-sample T-test or nonparametric Wilcoxon Rank-Sum test when appropriate. Suitably transformed variables will be used when necessary. Categorical variables will be compared using chi-square tests or Fisher's exact tests. Separate baseline analysis will be done within black and white samples in this study.

To determine the effect of progressive nicotine content reduction (NCR) on cotinine and other biomarkers of smoking exposure in both black and white smokers of lower SES over the 18 week trial period: for each of the biomarkers and other outcome variables of interest, exploratory data analysis will be conducted within each time period and across. Results will be summarized by table and figures (such as boxplots). Profile plots will be generated to show the trajectory of variable across different time periods. The major analytical tool for addressing the specific aims of this study is linear mixed models with repeated measures. For each biomarker and other numerical outcome measures of interest, a linear mixed model for repeated measures will be fit to evaluate the main effects of time, group, and time-by-group interaction; treating baseline scores for outcomes as covariates. Known confounders will be included in the linear models, and other covariates will be included if their individual bivariate associations with both the group variable and outcome are significant at 10% level. The magnitude and direction of the difference between the treatment groups will be quantified by reporting the estimated least-square mean differences at each time point. Separate analysis will be performed in black and white samples individually. We will also test for a number of potential effect modifiers by pooling the trial data of white smokers and black smokers together. Interaction terms that do not reach statistical significance will be dropped from the final model.

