To determine the modifying effect of menthol on progressive nicotine content reduction and biomarkers: modification effects such as the menthol will be examined by incorporating the menthol-by-group interaction in the multi-variable linear mixed model. The three-way interaction of the menthol-by-group-by-time will be explored but will be removed from the model if not significant. If the menthol-by-group interaction were found significant then mean-profile plot will be used to show the interaction in details.

To determine the predictors of participant drop-out/relapse: it is hypothesized that compensatory smoking behavior as measured by smoking topography and expired carbon monoxide, a higher baseline nicotine dependence behavioral score and rapid nicotine metabolism phenotypes will be associated with drop-out/relapse. The status of drop-out/relapse will be combined with the length of time from randomization to drop-out/relapse or loss of follow-up to form a time-to-event type of variable. Participants who completed the randomization phase of study will be considered as censored records. Kaplan-Meier type analysis (for categorical predictors) or simple Cox proportional hazard regression model (for quantitative predictors) will be used to examine the bivariate associations between the possible predictors and time to drop-out. If a predictor has shown marginal significance (with p-value less than 0.10) in the bivariate analysis then it will be kept in the multiple regression analysis. A multi-variable Cox proportional hazard regression

model will be built to examine the effects of the predictors jointly for time to drop-out. The magnitude and direction of effectiveness will be quantified by the estimated hazard ratios with their 95% confidence intervals. The interaction between the predictors will be explored in the analysis but will be removed if not significant.

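### Section 9.2 plans only difference tests for effects expected to be absent (on cigarettes smoked, toxicant exposure, and modification by menthol), so a non-significant result could not support those statements

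*Combined protocol and SAP*

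**What the plan says.** Section 1.1, Aim 1a, combines two kinds of expectation. Gradual reduction "will lead to lower levels of blood nicotine metabolites and nicotine-derived" NNAL, which is a directional claim, "while not affecting cigarettes smoked per", which is a claim of absence. Aim 1b adds a second claim of absence: menthol is expected not to alter the effect on the biomarkers.

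Section 2.3 supplies a third: "The policy also requires that reduced nicotine cigarettes not increase exposure to tobacco smoke toxins and carcinogens". It stands beside two other requirements, reduced nicotine exposure and reduced dependence, and the paragraph closes with "This needs to be documented prior to the full endorsement of the policy [28] and will be the major focus of this proposal".

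For each numerical outcome, section 9.2 says that "a linear mixed model for repeated measures will be fit to evaluate the main effects of time, group, and time-by-group interaction", with the baseline value as covariate. The result is to be reported as "estimated least-square mean differences at each time point". Black and white samples are analysed separately; pooling is mentioned for testing effect modifiers. On those, "Interaction terms that do not reach statistical significance will be dropped from the final model". The only confidence intervals promised are for drop-out: "estimated hazard ratios with their 95% confidence intervals". Section 9.1 sizes the trial to detect differences in plasma cotinine and GSH. No equivalence or non-inferiority margin and no precision target appears anywhere.

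**The concern.** Failing to reject a zero difference is not evidence that the difference is zero or small. It may only mean that the estimate is imprecise, and the chance of that rises as participants are lost. A statement of absence needs an interval narrow enough to exclude differences that matter, and hence a prior decision on what matters. Section 9.2 has neither the interval nor the decision.

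The possibility is not remote. Section 2.2 describes an earlier trial in which the 0.3 mg yield cigarettes were followed by a rise in cigarettes per day and in CO. If the RNC arm showed a moderate rise that missed significance, the planned output would not tell a reader whether a relevant rise had been excluded. Likewise, a non-significant menthol interaction would be removed from the model, although its size and interval are what Aim 1b needs.

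**Working it through.** **Inputs from the documents.** Section 9.1: 70 per group within race, 280 completers (140 per arm pooled), 30% drop-out, alpha 0.05 (two-sided assumed), cotinine SDs of 120 and 116 ng/ml. Section 9.2: baseline as covariate, separate analyses by race.

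**Assumptions.** The documents give no SD or margin for cigarettes per day, CO or the non-nicotine toxicants, so results are in SD units. A true rise of 0.25 SD is used for illustration. Baseline correlation r is taken as 0.5 to 0.7. Calculations are for one visit and completers only.

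**1. The plan's own figure.** Two-sample t-test, 70 per group, SD 120: power is 81.0% for 58 ng/ml and 91.5% for 68 ng/ml. 280/(1 − 0.30) = 400. Section 9.1 reproduces, but it concerns detection of a cotinine difference only.

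**2. Precision.** The 95% half-width in SD units is t × √(2/n), multiplied by √(1 − r²) after baseline adjustment. √(1 − 0.5²) = 0.866 and √(1 − 0.7²) = 0.714.

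| Completers per arm | Unadjusted | r = 0.5 | r = 0.7 |
|---|---|---|---|
| 70 (one race) | 0.334 | 0.29 | 0.24 |
| 140 (pooled) | 0.235 | 0.20 | 0.17 |

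With an assumed SD of 6 to 10 cigarettes per day, the unadjusted within-race half-width is 0.334 × 6 = 2.0 to 0.334 × 10 = 3.3 cigarettes per day.

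**3. Chance that a true rise of 0.25 SD is non-significant.** This is 1 minus the power of the two-sample t-test at standardized effect 0.25/√(1 − r²), that is 0.25, 0.289 or 0.350.

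| Completers per arm | Unadjusted | r = 0.5 | r = 0.7 |
|---|---|---|---|
| 70 (one race) | 69% | 60% | 46% |
| 140 (pooled) | 45% | 33% | 17% |

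If only 50 per arm remained, the unadjusted figure would be 76%.

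**4. Menthol.** If 280 completers split evenly over the four arm-by-menthol cells (an assumption, 70 each), the unadjusted 95% half-width of the interaction contrast is 1.96 × √(4/70) = 0.47 SD. A non-significant interaction is then compatible with sizeable modification.

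**5. What a margin could achieve at this size.** Take a ratio margin of 1.20 for illustration only, a true ratio of 1, and a log-SD of 0.4, 0.5 or 0.6 (assumed). Power = Φ(ln 1.20/(log-SD × √(2/n)) − 1.96), with ln 1.20 = 0.182.

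| Completers per arm | 0.4 | 0.5 | 0.6 |
|---|---|---|---|
| 140 (pooled) | 97% | 86% | 72% |
| 70 (one race) | 77% | 58% | 44% |

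Section 7.2.2 says some biomarkers will be assayed only in selected subgroups. For those, power would be lower.

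**The case against.** The strongest reply is that these are expectations and not formal claims. Aim 1a is worded as an expectation, cigarettes per day is not among the endpoints in sections 1.2 and 1.3, and the sample size rests on cotinine. Section 9.2 promises the size and direction of each difference, not only a p-value. This stands as a limit on severity. It does not supply an interval or a rule for concluding absence.

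A reader might infer that the investigators will report a null result as confirmation. The documents do not say so; section 9.2 gives no rule of interpretation in either direction.

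A reader might also infer that no increase in toxins is by itself the trial's major focus. Section 2.3 applies that phrase to three requirements together, and the other two are directional claims that a difference test suits. The same holds for NNAL, the one carcinogen biomarker named in Aim 1a, which is expected to fall.

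The unadjusted figures overstate the problem, because section 9.2 adjusts for baseline and section 3.3.2 keeps data up to withdrawal. The adjusted figures answer the first point. A repeated-measures model and partial data could add some precision, which the documents do not allow one to quantify.

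Finally, compensation is watched: section 3.3.1 has individual thresholds for CO and cigarettes per day, and sections 11.7 and 21.7 provide six-monthly summaries to the study monitor. Harm is therefore not left to a null test. But these are individual safeguards and descriptive summaries, and do not estimate the absence of a group effect.

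**Conclusion.** The point holds as a mismatch between stated expectations of absence and a plan built only on difference tests. Following section 9.2 as written, a non-significant result could not support the statements on cigarettes smoked, on modification by menthol, or on no increase in toxin exposure. For a true rise of 0.25 SD, the test would miss it 60% to 46% of the time within race and 33% to 17% pooled, with baseline adjustment at an assumed correlation of 0.5 to 0.7 (69% and 45% unadjusted). These figures rest on the planned numbers of completers and on an illustrative effect size.

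The cotinine comparison is untouched. It would be tempting to add that the present size can support a 1.20 margin. The documents do not bear that out: it is true at best for the pooled sample with all completers assayed, while section 9.2 plans race-specific analyses, where power is 77% to 44%, and some assays are restricted to subgroups.

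**What to change.** In section 9.2:

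- Report 95% confidence intervals for the baseline-adjusted RNC minus UNC difference (or ratio) at Visit 9 for cigarettes per day, exhaled CO and the non-nicotine toxicant biomarkers that are assayed.
- Report the menthol-by-group interaction with its 95% interval whether or not it is significant.
- State that a non-significant test is not evidence of no effect.
- Conclude *no increase* for an outcome only if the upper 95% limit is below a margin that the sponsor fixes before unblinding.
- Conclude *not affecting* cigarettes per day, or *no modification by menthol*, only if both limits lie within prespecified margins, since these statements are two-sided. Otherwise report *inconclusive*.
- Keep the difference test for NNAL and the nicotine metabolites.

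Make no statement that the present sample size supports a particular margin unless it is worked out for the analysis set and assay subgroup concerned.

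The cost is SAP wording and the choice of margins. Visit 9 already collects CO, urine and cigarette logs, so no visit or sample is added. The downside is that some statements may end as inconclusive, especially within race. The rule deals with imprecision only. It does not correct bias if participants who compensate are more likely to leave, as Aim 2 hypothesizes.

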1.2. Primary Study Endpoints

1.2.1. Product compliance/drop-out

1.3. Secondary Study Endpoints

- 1.3.1. Nicotine and withdrawal symptoms- Fagerstrom Test for Nicotine Dependence, Hooked on Nicotine Checklist, Stages of Change, Minnesota Withdrawal Scale, Questionnaire on Smoking urges
- 1.3.2. Nicotine metabolites, smoke exposure biomarkers, oxidative stress biomarkers
- 1.3.3. Smoking topography (puff volume, puff count, puff duration, puff intensity)
- 1.3.4. Stress biomarkers (cortisol) and questionnaires (Kessler 6, Perceived stress, CESD)

2. Background

2.1. Scientific Background and Gaps

The Family Smoking Prevention and Tobacco Control Act (FSPTCA) [1] gave the Food and Drug Administration (FDA) jurisdiction over the regulation of all tobacco products including their nicotine content. It gives the FDA authority under Section 907 of the Federal Food, Drug, and Cosmetic Act (FDCA) to require standards for tar and nicotine levels to protect public health. It also bans cigarettes with flavoring additives except menthol. Under this act, a major strategy to reduce harm from tobacco is lowering the nicotine content and delivery down to levels at which they are no longer addictive. The effectiveness of this strategy needs to be demonstrated in different populations whose response to RNC cigarettes might be substantially mediated by personal or environmental factors. For example, blacks have a lower quit rate than whites, and low SES continues to be a major predictor of smoking. Low SES smokers may be particularly susceptible to smoking because they live in more distressed conditions. Low SES smokers are less likely to quit and are more highly dependent.

2.2. Previous Data

A randomized, parallel arm, semi-blinded study examined the effects of reduced nicotine cigarettes on smoking behavior, toxicant exposure, dependence and abstinence. Participants were assigned to one of three groups over a six week intervention period: 1) 0.05 mg nicotine yield cigarettes (Quest 3); 2) 0.3 mg nicotine yield cigarettes (Quest 2); or 3) 4 mg nicotine lozenge. Compensatory smoking behavior, biomarkers of exposure, tobacco dependence, and tobacco withdrawal and abstinence rate were assessed. Unlike the 0.3 mg cigarettes, 0.05 mg cigarettes were not associated with compensatory smoking behaviors as demonstrated by the reduction in number of cigarettes per day and carbon monoxide (CO) levels. On the other hand, 0.3 mg cigarettes led to an increase in cigarette per day and in CO. Both cigarette types led to significant reductions in cotinine levels. The 0.05 mg cigarettes and nicotine lozenge were associated with reduced carcinogen exposure. While no increases were observed for carcinogen exposure with the 0.3 mg nicotine cigarette, the only significant decrease occurred for total NNAL. No significant changes were observed for cardiovascular measures. Both 0.05 mg nicotine cigarettes and nicotine lozenge were associated with reduced nicotine dependence and no increase in product withdrawal scores, whereas the 0.3 mg nicotine cigarettes resulted in no change in nicotine dependence and an increase in withdrawal scores upon cessation. The 0.05 mg cigarette was associated with greater relief of withdrawal from usual brand cigarettes than the nicotine lozenge. The 0.05 mg cigarette led to a significantly higher rate of cessation than the 0.3 mg cigarette and a similar rate as nicotine lozenge [2].

A similar study conducted by the same group where experimental conditions were: 1) 0.05 to 0.09 mg nicotine yield cigarettes (Quest and Xodus); 2) 0.05 to 0.09 mg nicotine yield cigarettes (Quest and Xodus) plus nicotine patch; and 3) 21 mg nicotine patch. In the two conditions that involved very low nicotine content cigarettes, the results showed a reduction in number of study cigarettes smoked, levels of alveolar carbon monoxide levels, total nicotine equivalents and total NNAL, and a reduction in perceived risk for addiction. Upon cessation of the study products, significant increases in craving and changes in withdrawal symptoms were observed for all three conditions, with no significant differences across conditions[3].

Another research group conducted three studies using reduced nicotine content cigarettes. The three studies were: 1) a single cigarette crossover, comparing cigarettes of different nicotine content and yield; 2) a 6 week tapering study, where nicotine yields were decreased on a weekly basis; 3) a similar tapering study in which nicotine yields were decreased on a monthly basis. All studies found: 1) Systemic intake of nicotine reflected the nicotine content of the cigarettes, with only small degrees of compensation. That is, as nicotine content declined, nicotine intake declined proportionally; 2) No evidence of increased systemic exposure to carcinogens (NNAL; polycyclic hydrocarbons) with decreasing nicotine content; 3) No evidence of changes in biomarkers of cardiovascular disease with decreasing nicotine content[4-6]. The mean level of education in participants was college graduation (e.g. ~15-16 years of education) and nearly all subjects were white.

2.3. Study Rationale

Reducing the nicotine content in cigarettes to levels that are not reinforcing or addictive is considered a feasible national policy to reduce tobacco-related morbidity [7]. When considering a national policy, it is necessary to consider that the single greatest predictor of tobacco use is low SES [8, 9]. In a report to the Tobacco Related Disease Research Program (TRDRP) of California, a review of the literature showed that persons of low income, education, unemployed, working-class jobs, or living in medically underserved areas have the highest smoking rates [10]. The Centers for Disease Control reported that the adult smoking rate was 31% below the federal poverty level compared to 19% at or above the poverty level [11].

These differences are even more pronounced in women. Tobacco advertising and marketing practices target low socioeconomic populations. Low SES smokers have less financial access to standard of care treatment for nicotine dependence such as nicotine pharmacotherapy and are less likely to quit despite having similar quit attempts as high income smokers. While it has long been thought that Federal excise taxes are more likely to reduce smoking in low income smokers, recent data indicate that low SES smokers are not more likely to quit than higher income smokers, and thus bear a disproportionate percent of their income on cigarette taxes [12].

Low SES smokers also exhibit a greater degree of cigarette brand loyalty. The disparities in smoking rates between low SES and high SES are projected to be even greater in the future [13]. The incidence rate of tobacco-related cancers has been significantly higher in low SES smokers compared to higher SES smokers [14] even after adjustment for cigarettes per day [15-22]. This difference is likely accounted for by higher levels of nicotine dependence and associated toxin intake in low SES smokers. Lower levels of education are associated with higher levels of cotinine per cigarette smoked in the National Health and Nutrition Examination Survey (NHANES) and other data [23, 24]. This may reflect low income smokers' preference for higher nicotine yield cigarettes [14].

Smoking rates are higher in both low SES whites and blacks. Because blacks largely prefer mentholated cigarettes whereas whites predominantly smoke non-menthol brands, research on tobacco harm in blacks has focused on whether menthol is more dangerous than non-menthol cigarettes in terms of disease risk or nicotine dependence. Under section 907 (e) of the 2009

Family Smoking Prevention and Tobacco Control Act (FSPTCA), the FDA's Tobacco Products Scientific Advisory Committee (TPSAC) submitted a report to the Secretary of Health and Human Services (HHS) on the public health impact of mentholated cigarettes. The TPSAC concluded that menthol doesn't increase cancer risk relative to non-mentholated cigarettes. We showed that cotinine levels did not differ significantly between menthol and non-menthol smokers [25, 26]. The TPSAC recommended that removal of menthol from the marketplace would benefit public health, based on the high use of menthol cigarettes as a starter product in youths. Since most data indicate that menthol is unrelated to cotinine levels among smokers of commercially available cigarettes, the greater degree of nicotine dependence in blacks may reflect their higher representation in low SES populations. The FDA has not yet acted on the TPSAC recommendation. It is possible that menthol may affect nicotine uptake in smokers of RNC cigarettes.

The FSPTCA is based on the premise that making tobacco less or non-addictive will result in a reduction in harm from tobacco smoke [27, 28]. This premise would apply for all aspects of nicotine dependence including smoking onset in non-addicted youths and smoking cessation in current dependent smokers. Although it is well known that compensatory smoking behavior (e.g. more frequent puffs or inhaling deeper) limits the ability to reduce nicotine exposure, at least in commercially available higher nicotine cigarettes [29], the feasibility of progressively switching to low nicotine cigarettes was considered to be technically feasible by the American Medical Association and other authoritative groups [28, 30]. A broad-based policy needs to consider the diverse population of smokers who vary substantially by socio-demographic, economic and cultural factors that may affect nicotine dependence and the choice of tobacco products smoked. In an initial report by Benowitz et al. [4] of a randomized trial of a specially blended low nicotine cigarette with features similar to Marlboro brand cigarettes, 130 smokers progressively lowered their nicotine over a 6-month period. There was a concurrent decrease in exposure to nicotine or nicotine derived carcinogen biomarkers such as cotinine and NNAL. In this trial, the mean level of education in participants was college graduation (e.g. ~15-16 years of education) and nearly all subjects were white. A similar trial by Hatsukami et al. [2] of 165 smokers that used commercially available Quest cigarettes assigned to two different low nicotine cigarettes for 6 weeks had similar findings.

A potential policy measure of lowered nicotine exposure through reduced nicotine yield cigarettes needs to specifically address whether lowered nicotine tobacco products reduces nicotine exposure given that smokers undertake compensatory smoking behaviors to maintain constant nicotine intake. The policy also requires that reduced nicotine cigarettes not increase exposure to tobacco smoke toxins and carcinogens, as well as decrease the levels of physiological dependence and smoking behaviors associated with nicotine dependence. This needs to be documented prior to the full endorsement of the policy [28] and will be the major focus of this proposal.

Stress is the major reason why youths and adults smoke. Cigarette smokers report that cigarettes help them calm down and relax. However the relationship between stress and smoking is still not well understood. Nicotine increases physiological stress through activation of the hypothalamic-pituitary-adrenal (HPA) axis, producing the stress hormone cortisol. Studies indicate that smokers have higher salivary levels of cortisol throughout the day than nonsmokers (Figure 1, data from: Steptoe A et al. [31]). Cortisol is also elevated in adults with lower SES compared to higher SES adults, although the findings are not consistent [32]. Although smokers report immediately after smoking that they have reduced stress, the response is acute and may reflect a temporary relaxed state while taking a break. Studies show that within half an hour after smoking, reported psychological stress levels in smokers return to their normal high levels [33]. This is supported by data showing that quitters have reduced psychological stress levels compared to persons who continue to smoke [34]. In the current study, we suggest that an important endpoint in a reduced nicotine policy for all smokers, but particularly for low SES

smokers, is that physiological and psychological stress should not be increased but decreased in a reduced nicotine regimen. An assessment of whether the gradual reduction in nicotine content of cigarettes is associated with a reduction in stress is the major focus of Specific Aim 3 of this proposal.

In studying how different cigarettes affect nicotine dependence, cotinine is the most commonly used biomarker of nicotine uptake and exposure. It is easily measured by ELISA and discriminates with a high degree of precision exposure to mainstream smoke vs. environmental tobacco smoke. It is also used as a general marker of the dose of exposure. However, cotinine represents <15% of total urinary nicotine metabolites. Because the rate of nicotine metabolism varies among individuals and is associated with the degree of nicotine dependence, the genotypic and phenotypic variation of nicotine metabolism will likely be an important factor in determining in which smokers a nicotine reduction strategy might be successful. Examining metabolic phenotypes as predictors of participant drop-out/relapse will be the major focus of Specific Aim 2 of this proposal.

3. Inclusion and Exclusion Criteria

